5.8. Justification for Doses in Humans

Detailed calculations related to pulmonary deposited dose are provided in the **Investigator's Brochure Section 8.2.2**. In animals, pulmonary deposited dose (PDD) refers to the amount of drug reaching the lung tissue. Assuming a 100% deposition fraction, the equivalent measure in humans is respirable delivered dose (RDD). Pharmacologic activity of inhaled ARO-ENaC was determined in sheep, where dose dependent increases in mucociliary clearance were observed at doses of 0.04 to 0.5 mg of pulmonary deposited dose (PDD) per kg body weight dosed on each of days 1, 2, 3. This translates to human respirable delivered doses of approximately 3.0 mg to 30 mg in a 60 kg patient (0.05 to 0.5 mg respirable delivered dose per kg of body weight). Similar pharmacologic activity was seen in sheep when a single, larger dose of 1.7 mg PDD per kg was given on day 1, which translates to a human RDD of 102 mg in a 60 kg person.

Therefore, all dose levels evaluated in the AROENAC1001 study are expected to result in dose dependent pulmonary ENaC channel suppression and increasing pharmacologic activity using the proposed dosing schedule. Sheep pharmacology studies show efficacious acceleration of mucociliary clearance at 2 weeks post-dose, which wanes at 3 weeks post-dose and returns to baseline by 4 weeks post-dose. Thus, for patient cohorts receiving multiple cycles of ARO-ENaC, dosing frequencies of either 2 weeks or 3 weeks will be tested in this study.

In assessing the human risk associated with inhalation of ARO-ENaC, consideration must be given to both the potential to elicit systemic toxicity as well as pulmonary toxicity. The initial clinical evaluation of ARO-ENaC in the AROENAC1001 study evaluates two different dosing regimens: a 3-day dosing cycle (Days 1, 2, and 3) in healthy volunteer cohorts 1-5 which is repeated after a 3-week

interval (Days 22, 23, and 24) in CF cohorts 2b-4b; as well as one, single dose repeated at 2-week intervals (Days 1, 15, and 29) in CF cohort 6. Safety margin considerations are provided for the highest dose regimen (cohort 6) utilizing exposure (AUC) and NOAEL data generated from the 24-day toxicity studies where ARO-ENaC was dosed on Days 1, 2, 3, 22, 23, and 24. While these dosing schedules differ, the total number of doses given in clinical Cohort 6 is fewer and at less frequent intervals than the doses given in the nonclinical toxicology studies.

The maximum human dose in this initial clinical study is 1.5 mg respirable delivered dose (RDD)/kg body weight given as a daily dose on Days 1, 15, and 29, to subjects in cohort 6. Based on a 60 kg human, the total human therapeutic dose of ARO-ENaC would be 90 mg RDD. Assuming a standard human lung weight of 1 kg or 1000 g (Tepper 2016) results in a lung dose of 0.09 mg RDD/g lung weight. The 0.09 mg RDD/g lung weight value can then be compared to values from the animal study to derive safety margins for lung effects. In rats, the NOAEL was considered to be 10.1 mg pulmonary deposited dose (PDD)/kg body weight and based on an average terminal body weight of 0.323 kg, the total administered dose of ARO-ENaC was 3.26 mg PDD. Assuming a standard rat lung weight of 1.5 g (Tepper 2016) results in an ARO-ENaC dose of 2.17 mg PDD/g lung weight. In monkeys, the NOAEL was considered to be 9.9 mg PDD/kg body weight and based on an average terminal body weight of 2.3 kg, the total administered dose of ARO-ENaC was 22.77 mg PDD. Assuming a standard monkey lung weight of 22 g (Tepper 2016) results in an ARO-ENaC dose of 1.04 mg PDD/g lung weight. Comparing the anticipated maximum human dose, 0.09 mg RDD/g lung weight, to the NOAEL dose in rats, 2.17 mg PDD/g lung weight, and the NOAEL dose in monkeys, 1.04 mg PDD/g lung weight, yields safety margins for lung effects of approximately 24X in rats and 12X in monkeys (**Table 1**). These safety margins for lung effects exceed those considered adequate by the FDA, which are 10X in rats and 5X in monkeys (Tepper 2016).

A more conservative estimate of the human nominal inhaled dose than RDD is the delivered dose (DD). DD is the amount of drug aerosolized by the nebulizer, while RDD is the amount of aerosolized drug contained in droplets of a size suitable for penetration into the lungs. The maximum cohort 6 dose of 1.5 mg RDD/kg body weight results in 0.09 mg RDD/g lung weight and 0.164 mg DD/g lung weight. Comparison of the maximum human delivered dose, 0.164 mg DD/g lung weight, to the PDD at the NOAEL in rats and monkeys, results in the more conservative safety margin estimates for lung effects of 13X in rats and 6X in monkeys (**Table 1**). This more conservative estimate of safety margins for lung effects still produces margins considered adequate by the FDA (Tepper 2016).

Safety margins for systemic effects were calculated utilizing interim clinical PK data from the ongoing AROENaC1001 study, by comparing the estimated plasma AUC_{inf} following the highest planned human dose of approximately 90 mg RDD (3730 h*ng/mL) with the plasma AUC_{last} at the NOAEL in rats (61900 h*ng/mL), and at the NOAEL in female monkeys (38900 h*ng/mL) as well as male monkeys (58400 h*ng/mL). This results in a safety margin for systemic effects of at least 16.6X in rats (61900 h*ng/mL ÷ 3730 h*ng/mL), 10.4X in female monkeys (38900 h*ng/mL ÷ 3730 h*ng/mL), and 15.7X in male monkeys (58400 h*ng/mL ÷ 3730 h*ng/mL) (**Table 2**). These safety margins for systemic effects to support the proposed clinical dose when calculated by AUC comparisons exceed those considered adequate by the FDA, which are 1X in both rats and monkeys (Tepper 2016).

Collectively, the results of the in vitro and in vivo nonclinical safety studies, as well as the estimated safety margins for both systemic and lung effects, support the continued clinical development of ARO-ENaC at the dose levels planned in this study.

Table 1. Safety margins for lung effects using the maximum planned clinical dose of approximately 90 mg respirable delivered dose (RDD) in cohort 6

Human RDD ^a (mg/g)	Human DD ^a (mg/g)	Rat PDD at NOAEL ^b (mg/g)	Rat Safety Margin using RDD	Rat Safety Margin using DD	Monkey PDD at NOAEL ^b (mg/g)	Monkey Safety Margin using RDD	Monkey Safety Margin using DD
0.09	0.164	2.17	24	13	1.04	12	6

^a Clinical doses given on Days 1, 15, 29. RDD and DD reflect average daily dose.^b GLP toxicology study doses given on Days 1, 2, 3, 22, 23, 24. PDD reflects average daily dose.**Table 2. Safety margins for systemic effects using the maximum planned clinical dose of approximately 90 mg respirable delivered dose (RDD) in cohort 6**

Human RDD ^a (mg)	Estimated Human AUC _{inf} (h*ng/mL)	Rat AUC _{last} at NOAEL ^b (h*ng/mL)	Rat Safety Margin	Male Monkey AUC _{last} at NOAEL ^b (h*ng/mL)	Male Monkey Safety Margin	Female Monkey AUC _{last} at NOAEL ^b (h*ng/mL)	Female Monkey Safety Margin
92.1	3730	61,900	16.6	58,400	15.7	38,900	10.4

^a Clinical doses given on Days 1, 15, 29.^b GLP toxicology study doses given on Days 1, 2, 3, 22, 23, 24.

It is important to note that while weight-based safety margins are calculated based on animal PDD compared to human RDD or DD, the RDD and DD are **not** the dose loaded into the nebulizer device. The nebulizer loaded dose required to achieve a certain RDD depends on the efficiency of the nebulizer. A table converting RDD into actual nebulizer loading dose is provided (**Table 3**).

Table 3: Nebulizer loaded dose for each cohort

Cohort	Nebulizer Loaded Dose	Concentration	Loaded Volume for Nebulization	Approximate Nebulization Time	Calculated Respirable Delivered Dose (RDD)
1	20 mg	10 mg/mL	2.0 mL	3-5 min	2.9 mg
2	40 mg	10 mg/mL	4.0 mL	6-8 min	6.6 mg
2b	40 mg	10 mg/mL	4.0 mL	6-8 min	6.6 mg
3	65 mg	10 mg/mL	6.5 mL	13-15 min	12.5 mg
3b	65 mg	10 mg/mL	6.5 mL	13-15 min	12.5 mg
4	180 mg	40 mg/mL	4.5 mL	10-12 min	30.7 mg
4b	180 mg	40 mg/mL	4.5 mL	10-12 min	30.7 mg
5*	180 mg	40 mg/mL	4.5 mL	10-12 min	30.7 mg
6*#	490 mg (245 mg)	40 mg/mL	12.2 mL (6.1 mL)	30 min (15 min)	92.1 mg (46 mg)

*Doses for cohorts 5 and 6 represent the maximum potential dose, which may be decreased at the decision of the sponsor, based on existing data from prior cohorts.

*#Cohort 6 dose will require 2 nebulizations. Top line indicates total quantity and bottom line indicates quantity per nebulization (in parentheses)

6. STUDY OBJECTIVES AND ENDPOINTS

The objective of the study is to assess the safety, tolerability, pharmacokinetics of ARO-ENaC in normal healthy volunteers (NHVs) and patients with Cystic Fibrosis (CF).

6.1. Primary Endpoint

1. The incidence and frequency of adverse events over time through end of study using escalating multiple doses in NHVs and in CF patients.

6.2. Secondary Endpoints

1. Changes from pre-dose baseline in serum electrolytes in NHVs and CF patients as a safety measure.
2. Changes from pre-dose baseline in Forced Expiratory Volume (FEV1) in NHVs as a measure of safety.

3. Pharmacokinetics of ARO-ENaC in NHVs and in CF patients

6.3. Exploratory Endpoints

1. Changes from pre-dose baseline in FEV1 in CF patients
2. Changes from pre-dose baseline in lung clearance index (LCI) in CF patients
3. Changes from pre-dose baseline in the revised cystic fibrosis questionnaire (CFQ-R) in CF patients
4. Rate of pulmonary exacerbations in CF patients receiving ARO-ENaC versus PBO
5. Changes from pre-dose baseline in body mass index (BMI) in CF patients
6. Plasma metabolite identification in NHVs (reported in a separate report outside of this study)
7. Determination of urinary excretion and metabolite identification in NHVs (reported in a separate report outside of this study)
8. Changes from pre-dose baseline to Day 18 in expression of ENaC using bronchoscopic brush biopsy samples in NHVs
9. Changes from pre-dose baseline to Day 18 in expression of ENaC using bronchoalveolar lavage (BAL) samples in NHVs
10. Changes from pre-dose baseline to Day 18 in cytokine levels as well as cell count and differential in BAL fluid in NHVs

7. STUDY PLAN

7.1. Study Design

Normal Healthy Volunteers:

While ARO-ENaC is intended for use in CF patients, these patients suffer from frequent disease exacerbations and are frequently on multiple concomitant medications. For this reason, this study initially evaluates each dose level in a healthy volunteer population to generate a baseline understanding of safety in a population with normal physiology and without the confounding factor of concomitant medication use.

For NHVs, 4 cohorts of 6 eligible subjects (4 active: 2 PBO) will be evaluated at each dose level starting with Cohort 1. Cohort 5 will include 12 eligible patients (8 active: 4 placebo) who will be treated with a dose equal to or less than that given to cohort 4, with the purpose of collecting bronchoscopic samples to evaluate for α ENaC mRNA knockdown. Participants who have signed an IRB/EC approved informed consent form and have met all of the protocol eligibility criteria during screening, will be randomized to receive ARO-ENaC or PBO. NHV cohorts will receive a single cycle of three doses all at a fixed dose level administered daily on Days 1, 2, 3.

NHV cohorts 1-4 will begin with administration of ARO-ENaC or PBO to two sentinel participants (one ARO-ENaC, one PBO). Following the Day 4 evaluation in these participants, if there are no significant safety concerns based on PI's judgement, the remaining participants in the cohort will be dosed. Cohort 5 will not utilize sentinel participants as the dose evaluated in cohort 5 will be equal to or lower than doses used in cohorts 1-4. Dosing of participants will be staggered by at least 30 minutes such that no two participants will be dosed simultaneously. Blood samples will be drawn pre-dose on Day 1 for baseline measurements.

Based on observations for all NHV subjects in a cohort through Day 21, and experience from any prior cohorts (i.e. all cumulative available safety data), the DSC will meet to vote on the following (See Fig. 1):

1. Dose escalation to next NHV cohort
2. Initiation of CF cohort (Cohorts 2b, 3b, 4b) when applicable per **Figure 1**.

Escalation to the next highest dose level in NHVs will proceed in cohorts of 6 until the highest planned dose level is completed, or the trial is halted prematurely by the PI, DSC or Sponsor due to safety or other concerns.

Following an affirmative vote from the DSC meeting held during NHV cohort 4 allowing the opening of CF Cohort 4b, NHV cohort 5 may be subsequently opened for accrual. The primary purpose of cohort 5 will be to assess the effect of ARO-ENaC on α ENaC mRNA expression, with samples obtained via bronchoscopy. The dose in cohort 5 will be equivalent to or less than the dose utilized in cohort 4. Based on available safety data reviewed during prior DSC meetings, the Sponsor or DSC may adjust the dose in cohort 5 downward.

The DSC will consist of at least one study Investigator, Sponsor Medical Monitor, Sponsor pharmacovigilance lead, and an independent physician experienced in pulmonary drug development and/or early stage clinical trials.

Cystic Fibrosis Patients:

Cohorts 2b, 3b, 4b will enroll eligible CF patients who have signed an IRB/EC approved informed consent form to receive two cycles of ARO-ENaC or PBO administered daily on Days 1, 2 and 3, then again on Days 22, 23 and 24. Screening for the CF cohorts can begin once Cohort 2 dosing has commenced but dose administration may not proceed until after the DSC has opened the designated CF patient cohort. CF patient cohorts 2b, 3b, and 4b will be opened for accrual once the corresponding NHV cohort receiving the same dose level has reached Day 21 and based on DSC vote that it is safe to proceed. CF patient cohorts 2b, 3b, and 4b will enroll in sequence with 2b enrolling first, followed by 3b and then Cohort 4b.

Once all subjects in CF cohort 4b have completed the Day 29 study visit, the DSC will meet to review all cumulative safety data to date and to vote on the initiation of CF cohort 6. Following an affirmative vote from this DSC meeting, CF cohort 6 may be opened for accrual. The purpose of cohort 6 is to assess the safety and efficacy of an alternate dosing regimen. In CF cohort 6, the 3- day dosing cycle used in cohort 4b is compressed to a single dose, which is given at 2 week intervals, such that subjects will be dosed on Days 1, 15, and 29. The dose given on each dosing day to a subject in CF cohort 6 (in respirable delivered dose [RDD] terms, which represents the amount of drug that reaches the lung, as opposed to the amount of drug loaded into the nebulizer) will be $\leq 3x$ the dose given on each dosing day to a subject in CF cohort 4b. Thus, the dose (in RDD terms) given on Day 1 to a subject in cohort 6 will be \leq the total cumulative dosage given over Days 1, 2, and 3 to a subject in cohort 4b. Of note, the RDD does not scale identically to the nebulizer loaded dose (i.e. tripling the RDD does not necessarily result in tripling the nebulizer loaded dose).

Blinding (where applicable) will be preserved to the extent possible. However, treatment un-blinding or un-blinding of an individual participant may occur, at the discretion of the PI or Medical Monitor, where deemed necessary for treatment of an AE or for a decision to be made regarding trial continuation. After all subjects in a cohort (except cohort 6) have completed an End-of-Study visit, Sponsor may be unblinded to that cohort. PI and study participants will remain blinded.

[figure not shown]
Primary analysis is planned once both all subjects in cohort 6 have completed the Day 43 visit and all subjects from other cohorts have completed EOS. PIs and study participants will remain blinded through EOS. Sponsor will be unblinded to analyze both safety and efficacy endpoints for all NHV and CF cohorts. Final Analysis is planned when all subjects ended study and database is locked. Safety and efficacy results will be updated based on complete database in final analysis.

Table 4: Cohort Summary

Cohort	Population	Blinding	# Subjects	Dosing Schedule
1	NHVs	Double-blind	6 (4 active: 2 PBO)	20 mg Day 1, 2, 3
2	NHVs	Double-blind	6 (4 active: 2 PBO)	40 mg Day 1, 2, 3
3	NHVs	Double-blind	6 (4 active: 2 PBO)	65 mg Day 1, 2, 3
4	NHVs	Double-blind	6 (4 active: 2 PBO)	≤ 180 mg Day 1, 2, 3
5	NHVs	Double-blind	12 (8 active: 4 PBO)	≤ 180 mg Day 1, 2, 3
2b	CF Patients	Double-blind	Up to 6 (4 active: 2 PBO)	≤ 40 mg dosed on Day 1, 2, 3; ≤ 40 mg dosed on Day 22, 23, 24
3b	CF Patients	Double-blind	Up to 6 (4 active: 2 PBO)	≤ 65 mg dosed on Day 1, 2, 3; ≤ 65 mg dosed on Day 22, 23, 24
4b	CF Patients (ppFEV1 > 70%)	Double-blind	Up to 12 (9 active: 3 PBO)	≤ 180 mg dosed on Day 1, 2, 3; ≤ 180 mg dosed on Day 22, 23, 24
6	CF Patients	Double-blind	Up to 24 (18 active: 6 PBO)	≤ 490 mg dosed on Day 1; ≤ 490 mg dosed on Day 15; ≤ 490 mg dosed on Day 29

The dose escalation schedule is outlined in **Figure 1**.

Figure 1: Dose Escalation Schedule

* Cohorts 1-4 each use 2 sentinel subjects dosed before the rest of the cohort. Where specified, dose represents the highest dose that may be used in the cohort. The DSC or Sponsor may adjust the dose downward if indicated based on available safety data.

† specified dose given once on Day 1, Day 2 and Day 3

** Cohorts 2b, 3b, 4b, and 6 enroll in sequence per Figure 1 and after associated DSC approval.

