7.4. Stopping Rules & Data Safety Committee

A decision to stop the trial early or discontinue drug in an individual subject, group of subjects or to halt enrollment temporarily or permanently may be indicated based on any of the following:

1. A single Serious Adverse Event (SAE, defined in Section 11.1) considered at least possibly related to study drug
2. Two cases of a drop from baseline FEV1 (which must be confirmed on repeat within 48 hours) **in healthy volunteer cohorts** of $\geq 20\%$ (absolute decline in % of predicted) considered to be at least possibly related to study drug by study investigator
3. One case of a drop from baseline FEV1 (which must be confirmed on repeat within 48 hours) **in cystic fibrosis cohorts** of $\geq 20\%$ (absolute decline in % of predicted) considered to be probably related to study drug by study investigator.
4. A post-dose increase in serum potassium to > 5.7 milliequivalents/Liter which must be from a non-hemolyzed sample and confirmed by repeat blood draw within 48 hours of initial results.

If any such events occur, within 5 days of Sponsor being notified of the event, the DSC will meet to review the event and determine any necessary actions as detailed below. Further dosing of the subject who triggered the stopping rule will be paused until such DSC review occurs.

Central labs will be utilized. However local labs may be utilized as necessary (including for Screening) if needed by the investigator or for emergent situations, including time critical analytes such as serum potassium and repeat clinical chemistries.

The Sponsor or PI can discontinue any subject at any time with or without DSC consultation. If such events (as described above) occur and the subject is not discontinued from the study the reason for not discontinuing the subject will be included in DSC meeting minutes. Including, but not limited to the events listed above, the DSC may pause the study to additional dosing or dose escalation to provide time to evaluate safety data and recommend the action to be taken, which may include, but is not limited to one of the following:

- Discontinuation of a subject or group of subjects from the study
- The study is stopped immediately with no further dosing
- The study will continue until the current cohort is completed
- The study will continue, but the next dose escalation will be to a level midway between the current level and the next planned level
- The study will continue as planned

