8.5. Restrictions and Concomitant Medications

- ***Confinement & Study visits:*** For NHV cohorts, clinical facility confinement will be approximately 4 days for single dose administration (Day -1 through Day 4 assessments in cohorts 1-4 and Day 0 through Day 4 in cohort 5). Subjects will be admitted to the facility on Day -1 (or Day 0 in cohort 5) and will undergo assessments at the facility on Days 1, 2, 3 and 4 prior to discharge. After Day 4 assessments NHV participants can be discharged and will return to the clinical facility starting on Day 5 for out-patient visits per the Schedule of Assessments (SOA). For CF patients, clinical facility confinement will be approximately 6 hours on dosing days unless additional monitoring at Principal Investigator (PI) discretion is needed for safety reasons. Patients will return to the clinical facility for outpatient visits. There is no planned overnight confinement for CF patients.
- ***Fasting:*** On the day of dosing or on other days with blood draws, participants will have fasted from food for at least 4 hours prior to study treatment administration or blooddraw unless otherwise specified or as otherwise required by study procedures. Fasting from food and drink will be required beginning at midnight on the night prior to a scheduled bronchoscopy, or as otherwise required by study procedures.
- ***Recreational Drugs & Alcohol:*** Participants will be instructed to abstain from consuming alcohol for at least 48 hours prior to admission, and while confined to the clinical facility. In addition, participants will be instructed to refrain from use of alcohol above these limits: >14 units per week for women or >21 units per week for men (1 Unit = 150 mL of wine, 360 mL of beer, or 45 mL of 40% alcohol) for the study duration. Participants must abstain from use of recreational drugs throughout the study.
- ***Concomitant Medications:*** NHVs and CF patients may not use prescription diuretics

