9.5. Allocation to Treatment

All potential participants who sign an informed consent at Screening will receive a unique 6-digit number (i.e. a Screening Number). The first 3 digits will represent the assigned site number and will be the same for each participant that screens at an individual site. The next 3 digits will be assigned sequentially (starting with 001). For patients who are deemed eligible, this 6-digit screening number will become the patient's permanent study ID number.

Eligible subjects in double-blind cohorts will be allocated a unique randomization number, in accordance with the randomization schedule. In each of NHV Cohorts 1-4, the first two subjects (sentinels) will be randomized separately to one active and one PBO. Each subject will be assigned to either active (ARO-ENaC) or PBO treatment. The allocation of active treatment or PBO will be performed using a block randomization algorithm.

Participants who drop out prior to their EOS visit for reasons other than an adverse event, may be replaced.

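### Cohort 6 starts a single-day RDD three times any earlier one with neither a sentinel pair nor a preceding same-dose volunteer cohort, and the protocol gives no reason for leaving sentinels out

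*Protocol*

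**What the plan says.** The protocol protects the first exposure to a new daily dose in two ways.

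- **Sentinels.** The Figure 1 footnote in Protocol Section 7.1 states that "Cohorts 1-4 each use 2 sentinel subjects dosed before the rest of the cohort". Section 9.5 adds: "In each of NHV Cohorts 1-4, the first two subjects (sentinels) will be randomized separately to one active and one PBO". The rest of the cohort waits for the sentinels' Day 4 evaluation. Cohort 5 is the stated exception: it "will not utilize sentinel participants as the dose evaluated in cohort 5 will be equal to or lower than doses used in cohorts 1-4".
- **A volunteer cohort first.** CF Cohorts 2b, 3b and 4b "will be opened for accrual once the corresponding NHV cohort receiving the same dose level has reached Day 21", subject to a DSC vote.

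Cohort 6 is described in the Synopsis, Protocol Sections 5.6, 7.1 and 10.1, and SAP Section 3.1. It opens on a DSC vote after all Cohort 4b patients reach Day 29. Section 7.1 caps the dose: "Thus, the dose (in RDD terms) given on Day 1 to a subject in cohort 6 will be" at or below the Cohort 4b total for Days 1 to 3. None of these places mentions sentinels or a staggered start for Cohort 6. The 30-minute spacing between participants appears only in the healthy-volunteer text.

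Under Section 7.4 the DSC meets within 5 days of the Sponsor being told of a trigger. The automatic step is limited: "Further dosing of the subject who triggered the stopping rule will be paused until such DSC review occurs". Pausing anyone else is at the DSC's discretion.

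**The concern.** Cohort 6 compresses three daily doses into one, so it is the first time anyone in the study inhales this much in a day. No volunteer cohort receives that single-day dose, and the cohort enrols at multiple sites in up to three countries. Section 8.5 says "There is no planned overnight confinement for CF patients", although patients stay in clinic for about 6 hours on dosing days.

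A well-tolerated 92.1 mg spread over three days supports the total. It does not show how patients tolerate 92.1 mg in one sitting, where an acute airway reaction or peak exposure would matter. Without a staged start, several patients at different sites could receive the new dose before anyone has seen the first patient's next-day examination, laboratory results and spirometry.

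**Working it through.** **Inputs.** RDD, loaded dose and volume: Protocol Section 5.8, Table 3. Cohort 6 allocation, 18 active to 6 placebo: Section 7.1, Table 4. Margin inputs: Section 5.8. Event probabilities of 0.2 and 0.3: Section 12.1, Table 5.

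**Reproducing the plan's cap.** 3 × 30.7 = 92.1 mg, so the Cohort 6 maximum equals the Cohort 4b three-day total and 92.1 / 30.7 = 3.00. The stated cap is met exactly.

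**Step at each new highest single-day dose.**

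| Step | RDD ratio | RDD increase | Loaded-dose ratio | Loaded increase | Sentinels |
|---|---|---|---|---|---|
| Cohort 1 to 2 | 6.6 / 2.9 = 2.28 | 3.7 mg | 40 / 20 = 2.00 | 20 mg | Yes |
| Cohort 2 to 3 | 12.5 / 6.6 = 1.89 | 5.9 mg | 65 / 40 = 1.63 | 25 mg | Yes |
| Cohort 3 to 4 | 30.7 / 12.5 = 2.46 | 18.2 mg | 180 / 65 = 2.77 | 115 mg | Yes |
| Cohort 4/4b to 6 | 92.1 / 30.7 = 3.00 | 61.4 mg | 490 / 180 = 2.72 | 310 mg | No |

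The Cohort 6 step is the largest as an RDD ratio and in milligrams on both scales. As a loaded-dose ratio it is slightly below the step from Cohort 3 to 4. The dose is split into two nebulizations of about 46 mg, each 46 / 30.7 = 1.50 times the Cohort 4b dose. Total volume rises 12.2 / 4.5 = 2.7-fold.

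**Reproducing the margins.**

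- Lung, on RDD: 2.17 / 0.09 = 24 (rat) and 1.04 / 0.09 = 12 (monkey).
- Lung, on delivered dose (DD): 2.17 / 0.164 = 13 and 1.04 / 0.164 = 6. The protocol treats 10 and 5 as adequate.
- Systemic: 61,900 / 3,730 = 16.6 (rat), 58,400 / 3,730 = 15.7 (male monkey) and 38,900 / 3,730 = 10.4 (female monkey), against 1.

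All agree with Tables 1 and 2 of the protocol.

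**Active patients exposed before the first next-day result.** The enrolment pace is not stated, so let *m* be the number who start before that result.

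- As written, the expected number active is 0.75*m*: 1.5, 3.0 or 4.5 for *m* = 2, 4 or 6.
- With a sentinel pair it is exactly 1.
- Chance that the first two patients are both active: unblocked, 18/24 × 17/23 = 0.55; in blocks of 4 at 3:1, 3/4 × 2/3 = 0.50. Block size is not stated. With a sentinel pair the chance is 0.

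**What one pair can show.** With a per-patient event probability of 0.2 or 0.3, the single active sentinel has an event with that same probability, so no event is seen 80% or 70% of the time. If four patients start early, the expected number with events is 3 × 0.2 = 0.6 or 3 × 0.3 = 0.9, against 0.2 or 0.3 with the pair. The main gain is the limit on early exposure; detection is modest.

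**The case against.** The case for the plan is substantial. No CF cohort uses sentinels, and Cohort 6 has its own dose rationale: the cumulative cap, a single sheep dose translating to a human RDD of 102 mg (above 92.1 mg), and a DSC review of all data through Cohort 4b Day 29. On delivered dose, the comparison "results in the more conservative safety margin estimates for lung effects of 13X in rats and 6X in monkeys", which still meets the protocol's benchmarks. The RDD-based and systemic margins are wider, and the human AUC estimate draws on interim clinical PK data from this study. Patients stay about 6 hours, with post-dose spirometry and an ECG. The Sponsor or PI may discontinue a subject without consulting the DSC, and the dose may be lowered. All of this stands, and it lowers the risk. It does not pace the first exposures, and the DSC's opening vote rests on human data up to 30.7 mg a day.

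A reader might infer four stronger points that the documents do not support:

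- **That the protocol's reason for omitting sentinels fails in Cohort 6.** That reason is offered for Cohort 5 only. For Cohort 6 there is simply no stated reason.
- **That this is the largest step on every scale.** It is not on the loaded-dose ratio, and Section 9.1 defines the protocol dose as the loaded dose.
- **That all 18 active patients would be exposed unchecked.** Nothing in the text prevents it, but it would require all of them to start within about a day. It is a theoretical ceiling.
- **That Cohort 4b's ppFEV1 limit above 70% was a safety step now skipped.** Sections 5.6 and 7.2 attribute it to the feasibility of LCI testing. Cohort 6 does admit 40-90%, so caution in patients at 70% or below is reasonable, but a separate sentinel pair for them is a preference.

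It is also fair that a Day 2 check comes one day after first exposure, whereas sentinels in Cohorts 1-4 had three days, and that delayed effects would be missed.

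**Conclusion.** The point holds as a cheap safety improvement. Cohort 6 takes a 3.00-fold single-day RDD step (+61.4 mg) with neither safeguard that the protocol uses elsewhere at first exposure, and without saying why. The existing controls do not limit how many patients receive the new single-day dose before the first next-day result.

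The documents do not show that the dose is unsafe or that the margins are inadequate. The exposure figures depend on an unstated enrolment pace and block size, and the step is smaller if the Sponsor lowers the dose. The Figure 1 drawing, the DSC charter and the Study Procedure Manual were not available. If one of them already requires a staggered start, the protocol only needs to say so. No sample-size figure is affected.

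**What to change.** 1. In the Cohort 6 text of the Synopsis and Protocol Sections 7.1 and 10.1, start the cohort with one sentinel pair: one ARO-ENaC and one placebo, randomized separately as in Section 9.5. Preferably both have Screening ppFEV1 above 70%, to match Cohort 4b.
2. Dose other patients only after the pair's Day 2 visit shows no significant safety concern and the Medical Monitor has confirmed this to all sites.
3. If a sentinel meets a Section 7.4 trigger, dose no further Cohort 6 patient until the DSC has met.
4. Add Cohort 6 to the Figure 1 footnote and to the sentinel sentence in Section 9.5, and align SAP Section 3.1.

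A second pair, or a hold to Day 8, for patients with ppFEV1 of 70% or less is optional.

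**Cost.** No patients, visits or procedures are added: Table 1.4 already has a Day 2 visit with examination, vital signs, laboratory tests and spirometry. Start-up is delayed by the time to enrol the pair, the day to the visit, and laboratory turnaround, which may exceed a day because central laboratories are the default. The remaining allocation becomes (18 − 1):(6 − 1) = 17:5, so the blocks must be reset before the cohort opens. The total stays 18:6, so the ppFEV1 sample size is unchanged.
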